	
assigned into two groups and Group 1 (transitioning to the investigational device) will perform functional tests (6MWT, L-test, Borg scale, AMPro) and answer questionnaires on the performance of their current prosthesis to provide baseline information. The Group 1 subjects will be fitted and trained on the investigational device and a recommended prosthetic foot which they will use as their prescribed prosthesis for 2-3 weeks until the second visit, the other half will stay on their prescribed prosthesis until the second visit.
 
During the second visit the subjects of Group 1 will perform the same functional tests as in the first visit (6MWT, L-test, Borg scale, AMPro) on the investigational device and answer questionnaires on the performance of the investigational device, and then return to their prescribed prosthesis. The Group 2 will perform the same tests/questionnaires on their prescribed prosthesis and then be fitted and trained on the investigational device and use it as their usual prosthesis for 2-3 weeks.
 
During the third visit all subject will repeat the tests and questionnaires on the prosthesis they are fitted with (Group1 on the prescribed and Group 2 on the investigational device). Subjects will have the option to use the investigational device for an additional 8-12 weeks, those who choose that will be fitted with the investigational device or will stay on it, depending in which they are in at this point. They will be booked for the fourth visit; they will be contacted via telephone 4-5 weeks later and asked to provide feedback on their experience with the device so far. Those that choose not to keep using the investigational device will be returned to their prescribed prosthesis.
 
During the fourth visit subjects will answer the same questionnaires and perform the same functional tests as the other visits. Data will be collected from the knee on activity. They will then be fitted back to their prescribed prosthesis.
 
End of study.
 
CPO subjects will answer a questionnaire on the ease of setup of the investigational device and provide feedback on the ease of setup of gait functions.
 
See Table 1 below.
								
--	---	--	--	--	--	--	--	--	--

Table 1 Summary of procedures and visits

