#### Visit 1:

The subject will be consented and enrolled after verification of the inclusion/exclusion criteria. Potential risk of participating in the investigation will be explained to the subject.

The LPI will communicate to the study monitor the number of users he has identified that meet the inclusion criteria and are willing to participate.

Subjects will be randomized into 2 groups, using a random number generator. Half of the subjects (Group 1) will then be fitted with the investigational device. Prior to fitting the subjects of Group 1 will be asked to provide feedback on the current prosthesis, by filling in a set of questionnaires **and performing the AMPro, L-test and 6MWT with Borg scale**, to obtain baseline data. Subjects may be videotaped during fitting and while performing functional tests, care will be taken to blur out faces and other personally identifiable markers such as tattoos and birthmarks.

Users will be fitted within the standard methods of prosthetic fitting, alignment, introduction, training and walking on various terrain. After being fitted with the investigational device subjects will receive functional training on the investigational device prior to going home and using it as their usual prosthesis for approximately 2-3 weeks. They will be given an appointment for the follow up visit prior to leaving the testing site.

The other half (Group 2) will stay on their prescribed prosthesis until the next visit in 2-3 weeks.

CPO subjects will provide feedback on the ease of setup and fitting, they will also be videotaped during setup. Care will be taken to blur out faces and other personally identifiable markers such as tattoos and birthmarks.

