#### Visit 2:

During the second visit subjects in Group 1 will perform the same functional tests as in the first visit (**6MWT, L-test, Borg scale**) on the investigational device and answer questionnaires on the performance of the investigational device, and then be fitted back to their prescribed prosthesis. Subjects in Group 2 will perform the tests/questionnaires on their prescribed prosthesis and then be fitted with the investigational device. A new appointment is made after approximately 2-3 weeks.

CPO subjects will provide feedback on the ease of setup and fitting.

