**iii) Measurements and data collection**

The same questionnaires, consisting of four valid instruments (PMQ, PEQ, PLUS-M, Borg) and in-house questions on the performance of the investigational device, will be used and filled in at three-four separate points in time. The same functional tests (L-test and 6MWT) will also be carried out at two points in time (except for those that elect the optional 8-12 week follow up period, there will be an addition visit with data collection and a follow up phone interview), the AMPRO will be performed at baseline to verify users K-level. The activity report will be generated from the Investigational device software application. See Table 6 for visit schedule and study procedures. **Table 6 Visit schedule and procedures**

Procedure/activity	Recruitment phase: 2-6 weeks prior to baseline	Group 1 visit 1: Baseline	Group 2 visit 1: Baseline	Group 1 visit 2: 2/3w F/U	Group 2 visit 2: 2/3w F/U	Group 1 visit 3: 4/6w F/U	Group 2 visit 3: 4/6w F/U	Visit 4 Optional 8-12w F/U
Potential subjects identified, fitting inclusion/exclusion criteria, by PI from customer database	X							
PI calls potential subjects and pre-screens by telephone	X							
Subject signs ICF, randomization		X	X					
Fitting, Training		X			X			
Subject fills in questionnaires		X		X	X	X	X	X
Subject performs 6MWT w/Borg scale and L-test		X		X	X	X	X	X
PI prints out activity report from investigational device				X			X	X
Subjects that choose to keep using the investigational device are given an appointment in 8-12 weeks from visit 3. Others are fitted with their prescribed prosthesis and end participation.						X	X	

All subjects still active are fitted back to their prescribed prosthesis, end of study.	X
CPO subjects provide feedback on fitting the investigational device	X

For each subject there are three scheduled visits to the study site and questionnaires/tasks/measurements administrated three times during the course of the study, with an additional 4th visit which is optional.

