## 10 Statistical Considerations

### 10.1 Statistical design and procedures

Outcomes at each timepoint will be visually inspected for normality using histograms and qq-plots. If the data are deemed to be normal the hypotheses will be tested using a two-tailed, paired, student's t-test. Non-normal data will be tested using the Wilcoxon signed-rank test.

Acceptance criteria for the data, as applicable, is defined in Table 4 **Endpoints, test methods and hypotheses**. Subgroup analysis will not be performed as no subgroups are defined.

Repeated measures analysis has the advantage of increased power vis-à-vis group allocations and reduction in error variance associated with individual difference, as each subject acts as its own control. This is important for studying amputees as the group is a small proportion of the total population, and with specific inclusion/exclusion criteria the total eligible population becomes very small, making it difficult to find and recruit subjects to attain an acceptable level of power. This limited population pool often results in slightly heterogeneous sample, as the amputees available are few and far between, in every sense. Furthermore, no single amputation procedure and therefore amputated stump is exactly the same, making the experience of each amputee a bit unique. The within-subject design significantly reduces the individual differences when comparing the two conditions.

The drawback of the design is the potential of "carryover effects", i.e. experience from one condition can affect outcome or performance in the other condition, creating a confounding extraneous variable that varies with the independent variable. Such effects are: practice, positive carryover effect to the latter condition; and fatigue, negative carryover effect to the latter condition.

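### Group 2 attends Visit 1 but is not tested there, so the device is always the second test session and a period term cannot separate it from practice

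*Combined protocol and SAP*

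**What the plan says.** Section 8.4 ii), Visit 1, has Group 1 tested before it receives the device: "Prior to fitting the subjects of Group 1 will be asked to provide feedback on the current prosthesis". The same paragraph adds the functional tests. Section 2 agrees: "Group 1 (transitioning to the investigational device) will perform functional tests". For Group 2 the Visit 1 text gives no test: "The other half (Group 2) will stay on their prescribed prosthesis until the next visit in 2-3 weeks".

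Table 6 matches. The row "Subject signs ICF, randomization" is marked for both groups at Visit 1. The row "Subject performs 6MWT w/Borg scale and L-test" is marked for Group 1 at Visit 1, blank for Group 2 at Visit 1, and marked in every later column. The questionnaire row has the same pattern.

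At Visit 2, "During the second visit subjects in Group 1 will perform the same functional tests as in the first visit", now on the device, while Group 2 is tested on its prescribed prosthesis and then fitted. At Visit 3 each group is tested on whatever it is wearing.

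Other text does not fit this schedule. Section 8.4 iii) says that every subject has "questionnaires/tasks/measurements administrated three times during the course of the study", which Table 6 contradicts for Group 2. The same section says that the functional tests are done on two occasions, which Table 6 contradicts for Group 1. Section 8.2 can be read as giving every subject a baseline evaluation of the comparator.

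Section 10.1 recognises order effects: "Such effects are: practice, positive carryover effect to the latter condition", with fatigue listed beside it in the opposite direction. The planned analysis is a paired t-test or Wilcoxon signed-rank test, with no period or sequence term. Section 7 places the comparator mean at two weeks and does not say which Group 1 visit supplies it.

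**The concern.** A two-sequence crossover deals with practice by balance: each treatment is tested once at each stage, and a common period effect cancels between the sequences. That requires subjects seen at the same visit to have taken the test equally often. Here they have not. At Visit 2, Group 1 is at its second session and Group 2 at its first. At Visit 3, Group 1 is at its third and Group 2 at its second. Adjusting for visit does not adjust for the number of tests taken.

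At stake is the comparison of device with comparator on the primary endpoint (Borg change over the 6MWT) and on 6MWT distance. If repeating the test changes these scores, part of that change can be reported as a device effect, or can hide one. No later analysis can recover the session that was not held.

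**Working it through.** **1. The plan's own figure.** Section 10.2 gives dz = 0.7084529, one-sided alpha 0.05, n = 15, power 0.8150214. With the A.R.E. factor 3/pi, the effective n is 15 × 0.95493 = 14.324, df = 13.324, delta = 0.7084529 × √14.324 = 2.6813, critical t = 1.7676 and power = 0.8150. The figure is reproduced. It makes no allowance for session effects.

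**2. Sessions under the schedule** (section 8.4 ii and Table 6).

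| | Visit 1 | Visit 2 | Visit 3 |
|---|---|---|---|
| Group 1 | comparator, session 1 | device, session 2 | comparator, session 3 |
| Group 2 | not tested | comparator, session 1 | device, session 2 |

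All device tests are at session 2, and nothing else is. With 15 subjects, a model with subject, session and treatment has 18 columns and rank 17, so treatment cannot be estimated. A model with subject, visit and treatment has full rank (18 of 18). It can be fitted, but it does not describe practice.

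**3. Bias with Visits 2 and 3 as the periods.** Let tau be the device effect, scored so that higher is better, and pi the Visit 3 minus Visit 2 period effect. Let L1, L2, L3 be the practice levels, assumed to depend only on the number of tests taken.

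- Group 1, device minus comparator: tau - pi + (L2 - L3)
- Group 2, device minus comparator: tau + pi + (L2 - L1)
- Average of the two: tau + L2 - (L1 + L3)/2 = tau + ½[(L2 - L1) - (L3 - L2)]

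The period effect cancels and the practice term does not. With P = L2 - L1:

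- no further gain after the first repeat: +0.50P
- second gain half the first: +0.25P
- equal gains: 0
- second gain twice the first: -0.50P

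If repetition worsens the score once and then levels off, P is negative and the bias goes against the device. Adding Group 1's Visit 1 data to a model with a visit term gives the same four values.

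As an illustration with assumed 6MWT gains, 20 m then 5 m gives 20 - 25/2 = +7.5 m, 12.5 m twice gives 12.5 - 25/2 = 0, and 5 m then 20 m gives 5 - 25/2 = -7.5 m.

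**4. Bias if Group 1's comparator is Visit 1.** Both groups then contribute L2 - L1, the comparator comes first in everyone, and the bias is the whole of P (20 m in the first illustration).

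**5. Effect on the error rate.** Simulation with 100,000 runs, 8 and 7 completers, no true device effect, one-sided 0.05 as in section 10.2 (section 10.1 says two-tailed). P is in SDs of the paired difference and is an assumption throughout. Columns 2 to 4 and 6 use Visits 2 and 3 with a period term. Column 5 is the plain paired test.

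| P | no further gain | second gain half | equal gains | Group 1 Visit 1 as comparator | worsens by P, then level |
|---|---|---|---|---|---|
| 0.1 | 0.070 | 0.060 | 0.051 | 0.100 | 0.034 |
| 0.2 | 0.102 | 0.073 | 0.051 | 0.182 | 0.022 |
| 0.3 | 0.136 | 0.085 | 0.050 | 0.296 | 0.014 |
| 0.5 | 0.233 | 0.118 | 0.051 | 0.580 | 0.005 |

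The planned unadjusted paired test on Visits 2 and 3 gives 0.071, 0.097, 0.125 and 0.201 in the no-further-gain case.

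**6. With Group 2 tested at Visit 1.** Session number equals visit number in both groups. The practice terms become L2 - L3 in Group 1 and L3 - L2 in Group 2, which average to zero for any practice curve. The false-positive rate returns to about 0.05, and one-sided power at n = 15 and dz 0.708 is about 0.83. Without a period term, 8 and 7 completers leave [8(L2 - L3) + 7(L3 - L2)]/15 = -(L3 - L2)/15.

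**The case against.** The strongest reply is that direction is not established. The bias is a curvature term: Group 1's third-session comparator works against the device and offsets Group 2's first-session comparator. A reader might infer that the schedule favours the device. The documents do not support that. They give no practice curve, and section 10.1 names fatigue beside practice without calling either the main confounder. For the primary endpoint, practice would have to alter the rise in Borg over the walk, and a practised subject who walks further might report more exertion. This part of the reply stands.

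Four further limits also stand.

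- The L-test endpoint in Table 4 is the proportion completing the test, set against 80%, with no comparator contrast, so the formula does not apply to it.
- Group 2's comparator session is its first in the study. Whether these established prosthesis users have taken the tests before is not documented.
- Group 2 does have a pre-device measurement, at Visit 2.
- Using Visit 1 as Group 1's comparator is the less natural reading, since section 7 refers to two weeks and section 8.4 treats Visit 1 as baseline. The plan should still say so.

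None of this removes the aliasing. A bias of unknown sign that the data cannot estimate remains a weakness in the primary comparison.

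**Conclusion.** The concern holds as a structural one. Under the schedule, device and second session coincide in every subject across Visits 1 to 3, and a period term leaves a bias of half the difference between the first and second practice gains. It can favour the device if gains diminish, vanishes if they are equal, and can go against the device if gains accelerate or an early worsening levels off. It bears chiefly on endpoints A and B.

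Size rests entirely on assumption. A gain of 0.2 SD that is complete after one repeat would about double the one-sided error rate (0.102 against 0.05), while equal gains would leave it unchanged. The algebra assumes that practice depends only on the number of tests taken and is the same in both groups. The change should be made before enrolment. With sign and size unknown for the Borg change, it is a should-fix rather than a must-fix. Separately, the conflicting counts of test occasions in section 8.4 iii) need reconciling with Table 6.

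**What to change.** - In section 2, Table 1, section 8.4 ii) Visit 1 and Table 6, have Group 2 complete the same questionnaires, 6MWT with Borg and L-test on its prescribed prosthesis as Group 1 does, before any subject learns the allocation. Treat Visit 1 as baseline and practice session for both groups.
- In section 7, state that Visits 2 and 3 are the two crossover periods and that Visit 1 does not supply the comparator value.
- In section 10.1, add a period term to the paired analysis, for example by averaging the two sequence-specific mean differences, so that practice cancels even with unequal completers.
- In section 8.4 iii), correct the statement on two functional-test occasions. The three-times statement then becomes true for every subject.

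The cost is one more run of an existing battery for about half of the 15 to 18 subjects (7 to 9), at a visit they already attend, with staff and equipment in place. No visit or subject is added; Visit 1 becomes longer for Group 2. The change balances practice from repeated testing. It does not remove carryover from wearing the device, which section 10.1 should continue to acknowledge.

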#### Visit 2:

During the second visit subjects in Group 1 will perform the same functional tests as in the first visit (**6MWT, L-test, Borg scale**) on the investigational device and answer questionnaires on the performance of the investigational device, and then be fitted back to their prescribed prosthesis. Subjects in Group 2 will perform the tests/questionnaires on their prescribed prosthesis and then be fitted with the investigational device. A new appointment is made after approximately 2-3 weeks.

CPO subjects will provide feedback on the ease of setup and fitting.

#### Visit 3:

During the third visit all subject will repeat the tests and questionnaires on the prosthesis they are fitted with. Subjects will have the option to use the investigational device for an additional 8-12 weeks, those who choose that will be fitted with the investigational device or stay on it, depending on which they are fitted with. They will be given an appointment for the fourth visit 8-12 weeks later. They will be contacted via telephone 4-5 weeks later and asked to provide feedback on their experience with the device so far, see script in **Appendix 18.1**. Those that choose not to keep using the investigational device will be fitted back on their prescribed prosthesis and end their participation in the study at visit 3.

**Visit 4 (optional):**

During the fourth visit subjects will answer the same questionnaires and complete the same functional tests as the other visits and data will be collected from the knee on activity (step count, use time). They will then return to their prescribed prosthesis. End of study.

**iii) Measurements and data collection**

The same questionnaires, consisting of four valid instruments (PMQ, PEQ, PLUS-M, Borg) and in-house questions on the performance of the investigational device, will be used and filled in at three-four separate points in time. The same functional tests (L-test and 6MWT) will also be carried out at two points in time (except for those that elect the optional 8-12 week follow up period, there will be an addition visit with data collection and a follow up phone interview), the AMPRO will be performed at baseline to verify users K-level. The activity report will be generated from the Investigational device software application. See Table 6 for visit schedule and study procedures. **Table 6 Visit schedule and procedures**

Procedure/activity	Recruitment phase: 2-6 weeks prior to baseline	Group 1 visit 1: Baseline	Group 2 visit 1: Baseline	Group 1 visit 2: 2/3w F/U	Group 2 visit 2: 2/3w F/U	Group 1 visit 3: 4/6w F/U	Group 2 visit 3: 4/6w F/U	Visit 4 Optional 8-12w F/U
Potential subjects identified, fitting inclusion/exclusion criteria, by PI from customer database	X							
PI calls potential subjects and pre-screens by telephone	X							
Subject signs ICF, randomization		X	X					
Fitting, Training		X			X			
Subject fills in questionnaires		X		X	X	X	X	X
Subject performs 6MWT w/Borg scale and L-test		X		X	X	X	X	X
PI prints out activity report from investigational device				X			X	X
Subjects that choose to keep using the investigational device are given an appointment in 8-12 weeks from visit 3. Others are fitted with their prescribed prosthesis and end participation.						X	X	

All subjects still active are fitted back to their prescribed prosthesis, end of study.	X
CPO subjects provide feedback on fitting the investigational device	X

For each subject there are three scheduled visits to the study site and questionnaires/tasks/measurements administrated three times during the course of the study, with an additional 4th visit which is optional.

## 8.5 Compensation

### iv) Subject

Amputee subjects will be compensated for their spent time in the clinic with [REDACTED] in the end of each visit. CPO subjects will not be compensated.

## 8.6 Responsibilities

### Sponsor Principal Investigator (Coordinating investigator)

- Identify sites
- Investigate possible vigilance cases/SAEs
- Train and explain the protocol to the sites
- Collect data via phone interview during optional 8-12w follow up

### Monitor

- Monitor trial
- Collect data
- Analyze results
- Write report

### Co-Investigator

- Collect Data
- Analyze results
- Write report
- Assist in conduct of trial procedures at investigators' site
- Assist in fitting users with trial device (and back to their prescribed prosthesis, if applicable)
- Perform reset and inspection of investigational devices between users (engineer).

### Local Principal Investigator at site

- Screen subjects
- Explain trial to participants
- Responsible for obtaining informed consent from test subjects
- Conduct all trial procedures at investigators' site
- Fit users with trial device (and back to their current prosthesis, if applicable)

## 8.7 Study monitoring and Oversight

The study monitor(s) will monitor the study to ensure all procedures are followed correctly and according to the study protocol. The study monitor will gather and review all study data and inform the PI of missing data or nonconformities to the study protocol.

The study monitor(s) and **LPI** will maintain communication on a minimum biweekly basis, via telephone and email. The **LPI** will provide the study monitor(s) with information of all scheduled study visits. The study monitor will visit the investigational site at least once while a study visit takes place.

## 9 Investigational Device Accountability

The investigational device will be provided as needed for the study population. Devices will not be packaged but will be labeled according to **FDA** regulatory requirements. Subjects will not be blinded.

The **LPI** will keep records documenting the receipt, use and return of the investigational device in the Investigational Device Management Form, including:

- Date of receipt
- ID of each investigational device
- Date of use
- Subject ID
- Date of device return
- Date of return of unused, expired or malfunctioning investigational devices, as applicable

